6. STATISTICAL ANALYSIS	21
6.1 Number of persons and justification.....	21
6.2 Strategy for analyzing collected data.....	21
6.2.1 Patient characteristics and follow-up	21
6.2.2 Criteria Studied.....	21
6.3 Statistical criteria for discontinuing the research.....	22

6.4 *Method of management of missing, unused or invalid data*..... 22

6.5 *Choice of persons to be included in the analyses*..... 22

6.6 *Data Analysis Manager and Working Software*..... 22

7 RIGHT OF ACCESS TO DATA AND SOURCE DOCUMENTS 23

8 LOGISTICS AND QUALITY ASSURANCE 23

9 LEGAL AND ETHICAL CONSIDERATIONS 24

9.1 *CNIL [French Data Protection Agency] Declaration* 24

9.2 *Information and Non-opposition Form* 24

9.3 *Final report on the Research* 24

10 DATA PROCESSING AND STORAGE OF DOCUMENTS AND DATA RELATING TO THE RESEARCH 24

11 RULES RELATING TO PUBLICATION 25

APPENDIX 1 : Opinion of HAS dated July 13, 2010 26

APPENDIX 2 : Information note to patients / HAS Guide 27

APPENDIX 3 : Normal surgical risk patient 28

APPENDIX 4 : High surgical risk patient 29

APPENDIX 5 : [REDACTED] 30

APPENDIX 6 : Composition of the Scientific Committee 43

APPENDIX 7 : Results of the Random Draw 44

APPENDIX 8 : References 45

CONTACTS & LIST OF INVESTIGATING CENTERS

[REDACTED]

[REDACTED]

[REDACTED]

[REDACTED]

List and details of the implant centers

SUMMARY OF THE STUDY

Study title :

Study of the GORE® EXCLUDER® Endoprosthesis in the treatment of infra-renal Abdominal Aortic Aneurysms

Introduction :

The treatment of Infra-renal Abdominal Aortic Aneurysms can be effected by abdominal aortic stenting introduced via the femoral artery. This technique is widely used in high surgical risk patients, but may also be recommended for normal surgical risk patients under certain conditions. Given the information available, the French National Authority for Health requires a 5-year follow-up as part of the renewal of reimbursement for these endoprosthesis.

Rationale:

The use of abdominal aortic endoprosthesis makes the treatment of Infra-renal Abdominal Aortic Aneurysms possible, with implantation via the femoral artery, thus avoiding a very invasive surgical procedure.

However, we lack data on the future of these endoprosthesis in the long term.

For this reason, an observational long-term (5 years) study has been put in place.

Objective:

The objective of this study is to assess the usefulness of the technique by documenting overall mortality, complications (endoleak, migration), the rate of surgical conversion, the evolution and rupture of the aneurysm, in the long term, that is, 5 years, on a cohort of patients representative of the population treated in real life conditions.

Judgment criteria:

These criteria are measured postoperatively or within one month after surgery, at 6 months, 12 months and then annually for 5 years, with an annual report issued to be submitted to the French National Authority for Health:

- Overall mortality rate,
- Mortality rate related to the aneurysm,
- Evolution of the diameter of the aneurysm
- Rate of type I, II and III endoleaks,
- Migration rate,
- Rate of surgical conversion,
- Rate of endovascular or surgical re-intervention.

Methodology, type of study:

Observational, Prospective, Multicenter Study

Study Device:

The device concerned in the study is the GORE® EXCLUDER® Endoprosthesis, and any evolution of the range included in the LPP.

Inclusion Criteria:

Any patient requiring abdominal aortic stenting for the treatment unruptured Infra-renal Aortic Abdominal Aneurysm.

Non-inclusion Criteria

Patients whose clinical follow-up is not possible, i.e., patients who cannot return for control visits (e.g. patients living abroad).

A register to document each patient not included in the cohort will be established.

Conduct of the Study:

Following the same schedule as that of patient routine follow-up, that is, with a postoperative follow-up or within one month after surgery, at 6 months, 12 months and then annually, for 5 years.

	Post-operative follow-up (D1 to D30)	Follow-up at 6 months.	Follow-up at 1, 2, 3, 4 and 5 years	Follow-up intermediate ***
Clinical examination	X	X	X	X
Radiography of the abdomen without preparation in 3 effects (front, profile and ¾)	X ¹	X*	X*	X*
CT with contrast medium	X	X	X	X
MRI	X*	X*	X*	X*
Vascular Doppler	X**	X**	X**	X**

* if CT with contrast medium cannot be performed

** if RMI cannot be performed

*** interim follow-up carried out only in case of leakage, deterioration of the endoprosthesis or scalability of the aneurysm on the previous control examination. Follow-up to be carried out 3 months after the control where the anomaly was observed.

¹ Radiography in postoperative follow-up will not be necessary in case of 3D reconstruction performed during the CT.

Expected Benefits:

The expected benefit of this Study is to have a long-term evaluation of Abdominal Aortic GORE® EXCLUDER® Endoprosthesis, thus making it possible to assess the long term usefulness of the technique with this endoprosthesis.

[REDACTED]

Known Risks:

The protocol does not affect patient management, so there is no risk posed by the research.

Duration of the inclusion period:

Inclusion period of 180 patients: 12 months

Duration of participation of each patient:

The requirement of the French National Authority for Health is long-term patient follow-up, that is, 5 years. In this context, there is no maximum follow-up duration for this study.

Total duration of the Research:

In this context, there is no maximum follow-up duration for this Study (12 months inclusion period and a minimum of 5 years of follow up).

[REDACTED]

[REDACTED]

[REDACTED]

[REDACTED]

[REDACTED]

[REDACTED]

1 SCIENTIFIC JUSTIFICATION AND GENERAL DESCRIPTION OF THE RESEARCH

1.1 Rationale¹

1.1.1 General Description of the Disease and of its Management

Definition

There is no unambiguous definition of an Abdominal Aortic Aneurysm (AAA). For Johnston *et al.*², AAA is a localized and permanent dilation of the aorta of more than 50% compared to the normal expected diameter, with a loss of parallelism of its edges, bag-shaped (saccular aneurysm) or spindle (fusiform aneurysm). This definition helps to differentiate an AAA from an “Arteriomegaly” (diffuse enlargement affecting several arterial territories with a diameter exceeding 50% of the expected arterial diameter). The normal diameter of the aorta is fundamental data. It depends on age and sex.

Other definitions have been used in the literature. For Cronenwett *et al.*³, an Infra-renal Abdominal Aortic Aneurysm is an enlargement of its transverse or anteroposterior diameter by more than one and a half times that of the interrenal aorta. Collin *et al.*⁴ proposed the following definition: “An abdominal aortic aneurysm is present when the maximum external diameter of the infrarenal abdominal aorta is either (1) greater than 4.0 cm or (2) exceeds the maximum diameter of the aorta between the origin of the superior mesenteric and left renal arteries by at least 0.5 cm.”

The risk of progression of AAA has been studied mainly in relation to its maximum outside diameter, a value commonly used to determine the rate of growth, the risk of rupture of an AAA, and to define the surgical indications.

Similarly, descriptions of “small,” “medium” or “large” are based on commonly accepted figures⁵:

- A ‘small’ AAA has a diameter smaller than 5 cm.
- An ‘average’ AAA has a diameter between 5 and 7 cm.
- A ‘large’ AAA has a diameter of more than 7 cm.

Severity¹

The progressive growth of an AAA is inevitable, but the pace of this growth is difficult to predict in a given patient. Thanks to diagnosis and monitoring methods, surgery is increasingly programmed at an early stage^{6,7}. This helps prevent rupture which is a progressive form evaluated at 7 per 100,000. This is a common cause of death in patients with Abdominal Aortic Aneurysm.

1.1.2 Treatment

There are two types of treatments:

- **Endovascular treatment with stenting.** The principle of endovascular treatment of AAA is based on the exclusion of the aneurysm with an endoprosthesis inserted via the femoral artery and attached to the artery walls upstream and downstream.

The theoretical advantages of this alternative to conventional therapy are the absence of laparotomy, aortic clamping and reduced blood loss. This technique is less invasive than conventional surgery⁸. This technique is accompanied by the need for a significant number of additional procedures. Initially, uncertainties existed on the durability of implants and evolution of the AAA towards rupture even though aortic endoprosthesis implantation is still possible⁸. However, the publication of long term results of the EVAR1⁹ and 2¹⁰ Studies in 2010 as well as the DREAM Study¹¹, dispelling these uncertainties to a large extent by providing long term results.

- **Surgery by flattening transplant** with opening of the aneurysm sac and implantation of a synthetic or bifurcated tube, whose perioperative mortality is currently less than 5% in the majority of unruptured AAA series^{12,13}. Mortality increases significantly, up 15%, in high surgical risk patients. This surgery may be combined with treatment of associated lesions of visceral arteries.

The treatment of Abdominal Aortic Aneurysms by laparoscopic surgery is a new technique currently being evaluated.

1.1.3 Requirements of the French National Authority for Health

The opinion of the National Commission for the Evaluation of Medical Devices and Health Technologies (CNEDiMTS) of July 13, 2010 (Appendix 1) indicates that:

Terms of renewal:

CNEDiMTS subjects the renewal of registration of each endoprosthesis to the presentation of results of a specific follow-up study implemented on a cohort of patients representative of the population treated in real life conditions.

The objective of each study is to evaluate the usefulness of the technique by documenting overall mortality, complications (endoleak, migration), the rate of surgical conversion, evolution and rupture of the aneurysm, in the long term, that is, beyond 5 years.

This prospective cohort study shall involve at least 150 patients implanted after registration on the LPPR [List of Reimbursable Products and Services].

The results of the follow-up study shall be forwarded to CNEDiMTS once a year, for consideration.

The follow-up evaluation may lead CNEDiMTS to recommend that reimbursement for the abdominal aortic endoprosthesis concerned be maintained or suppressed.

1.1.4 Description of the GORE[®] EXCLUDER[®] Endoprosthesis

The device concerned in the study is the GORE[®] EXCLUDER[®] Endoprosthesis, and any evolution of the range included in the LPP.

The GORE[®] EXCLUDER Endoprosthesis[®] is an aortic, modular, bifurcated Endoprosthesis composed of two elements:

- the Trunk-ipsilateral Leg Endoprosthesis. (trunk) (Fig. 1 and 2)
- the Contralateral Leg Endoprosthesis (Fig. 3 and 4)

The prosthesis is in expanded polytetrafluoroethylene (ePTFE), supported by a Nitinol wire along its outer surface. Nitinol anchors and an ePTFE sealing cuff are located at the aortic end of the trunk. An ePTFE sleeve is used to constrain the endoprosthesis on the leading end of the delivery catheter (fig. 5, 6, 7 and 8).

Figure 1: Trunk-ipsilateral leg endoprosthesis; (aortic diameters of 23, 26 or 28.5 mm)

[figure not shown]

Figure 2: Trunk-ipsilateral leg endoprosthesis; (aortic diameters of 31 mm)

[figure not shown]
[figure not shown]

[figure not shown]
Figure 3: Contralateral leg endoprosthesis; (distal iliac diameters of 12 and 14.5 mm)

Marqueurs radio-opaques de l'endoprothèse jambage controlatéral :

- Un (1) marqueur à chaque extrémité

Figure 4: Contralateral leg endoprosthesis; (distal iliac diameters of 16, 18 and 20 mm)

Marqueurs radio-opaques de l'endoprothèse jambage controlatéral :

- Un (1) marqueur à chaque extrémité
- Un (1) marqueur situé à 3 cm en dessous de l'extrémité proximale
- Un (1) marqueur situé à 4 cm au-dessus de l'extrémité distale

Figure 5: GORE EXCLUDER® AAA Endoprosthesis Delivery Catheter

[figure not shown]

Figure 6: (Trunk-ipsilateral leg) GORE® EXCLUDER AAA Endoprosthesis undeployed on catheter with radiopaque markers

Figure 7: (Distal contralateral iliac diameters of 12 and 14.5 mm) GORE EXCLUDER® AAA Endoprosthesis constrained delivery catheter with radiopaque markers

[figure not shown]

Figure 8: GORE EXCLUDER® AAA Endoprosthesis (Contralateral iliac diameters of 16, 18 and 20 mm) constrained delivery catheter with radiopaque markers

[figure not shown]

Figure 9: Aortic Extender Endoprosthesis

[figure not shown]

Figure 10: Aortic Extender Endoprosthesis Delivery Catheter

[figure not shown]
[figure not shown]
[figure not shown]

Figure 11: Constrained Aortic Extender Endoprosthesis

The Iliac Extender Endoprosthesis provides an extension of up to 4 cm of either the ipsilateral or contralateral limb. The extender component can be placed at variable extension lengths from 4 cm to 0 cm, allowing a customization of extender treatment length based on patient anatomy. The graft material is ePTFE/FEP, supported by a Nitinol wire along its external surface. A radiopaque marker is located 3 cm from the proximal end (fig. 12). An ePTFE/FEP sealing cuff is used to constrain the endoprosthesis on the leading end of the delivery catheter (fig. 13). Deployment of the Iliac Extender initiates from the leading end and proceeds toward the trailing end of delivery catheter. Following deployment, the ePTFE / FEP remains *in situ* between the endoprosthesis and the vessel wall.

[figure not shown]
Figure 12: Iliac Extender Endoprosthesis

Marqueurs radio-opaques de l'extension iliaque (3 au total) :

- Deux (2) marqueurs d'extrémité : un (1) à chaque extrémité
- Un (1) marqueur situé à 3 cm en dessous de l'extrémité proximale
- * Remarque : Toutes les dimensions sont nominales.

Figure 13: Constrained Iliac Extender Endoprosthesis (distal iliac diameters of 10, 12 and 14.5 mm)

1.2 Expected Benefit

The expected benefit of this study is to have a long-term evaluation of the GORE® EXCLUDER Abdominal Aortic Endoprosthesis® thus allowing to evaluate the long term usefulness of the technique with this endoprosthesis.

This study will make it possible meet the HAS requirements for any renewal of registration on the LPPR of the GORE® EXCLUDER® Endoprosthesis (Appendix 1).

1.3 Foreseeable and known risks for persons participating in the research

The research is observational; it does not lead to any change in patient management. Consequently, there is no risk associated with the research for patients.

1.4 Description of the Study Population

The study population corresponds to 180 consecutive patients treated with bifurcated GORE® EXCLUDER Endoprosthesis® for unruptured Infra-renal Abdominal Aortic Aneurysm.

Patient recruitment shall be a consecutive recruitment of 180 patients. Each center is multidisciplinary, combining surgical and radiological activities.

2 OBJECTIVE OF THE STUDY

The objective of this Study is to evaluate the usefulness of the technique by documenting:

- Overall mortality,
- Complications (endoleak, migration),
- The surgical conversion rate,
- The evolution and rupture of the aneurysm,

in the long term, that is, 5 years, on a cohort of patients representative of the population treated in real life conditions.

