3.3 Evaluation Criteria

These criteria are measured postoperatively or within one month after surgery, at 6 months, 12 months and then annually for 5 years, with an annual report issued to be submitted to the French National Authority for Health:

- Overall mortality rate,
- Mortality rate related to the aneurysm,
- Evolution of the diameter of the aneurysm
- Rate of Endoleaks for Type I, II and III
- Migration rate,
- Rate of surgical conversion,
- Rate of endovascular or surgical re-intervention.

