3.4 Evaluation Parameters

General Data

- Age
- Gender
- Diameter of Abdominal Aortic Aneurysm
- Patient status (normal or high surgical risk according to the Afssaps criteria, Appendices 3 and 4)
- All references and evolution of the range of the GORE® EXCLUDER Endoprosthesis®

Data related to the procedure (at all control times):

- Death from all causes
- Aneurysm-related death
- Evolution of the diameter of the aneurysm
- Types I, II and III endoleak
- Migration
- Surgical conversion
- Re-intervention related to the initial procedure

Definitions :

Death related to the aneurysm shall be defined as any death occurring as a result of a ruptured Abdominal Aortic Aneurysm or following any procedure intended to treat Abdominal Aortic Aneurysm.

If the death occurred within 30 days of any procedure intended to treat Abdominal Aortic Aneurysm, then it will be considered as related to the aneurysm unless proven otherwise. Deaths occurring beyond 30 days of any procedure intended to treat Abdominal Aortic Aneurysm and that are related to the procedure should be considered as related to the aneurysm.

Distal migration is defined by a distal displacement strictly greater than 10 mm. Proximal migration is defined either by proximal displacement strictly greater than 10 mm, or by proximal displacement which covers one of the renal arteries; the reference examination being the first postoperative CT performed.

An increased aneurysm diameter is defined as an increase strictly greater than 5 mm of the largest measurable diameter of the aneurysm; the reference diameter being the diameter of the first post-operative check-up.

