6.2.2 Criteria Studied

Main analyses:

The criteria studied are as follows:

- Death from all causes
- Aneurysm-related death
- Evolution of the diameter of the aneurysm.
- Types I, II and III endoleaks
- Migration
- Surgical conversion
- Re-intervention related to the initial procedure

Definitions :

- Death related to the aneurysm shall be defined as any death occurring as a result of a ruptured Abdominal Aortic Aneurysm or following any procedure intended to treat Abdominal Aortic Aneurysm.
If the death occurred within 30 days of any procedure intended to treat Abdominal Aortic Aneurysm, then it will be considered as related to the aneurysm unless proven otherwise. Deaths occurring beyond 30 days of any procedure intended to treat Abdominal Aortic Aneurysm and that are related to the procedure should be considered as related to the aneurysm.
- Distal migration is defined by a distal displacement strictly greater than 10mm. Proximal migration is defined either by proximal displacement strictly greater than 10mm, or by proximal displacement which covers one of the renal arteries; the reference examination being the first postoperative CT performed.

- An increase in the diameter of the aneurysm is defined by an increase strictly greater than 5 mm of maximum diameter of the highest measurable diameter of the aneurysm; the reference diameter being the diameter of the first post-operative check-up.

Each of the rates that match the Study criteria will be analyzed by calculating frequency distributions and bilateral confidence intervals of 95% (IC95) associated.

Event rates over time are described by survival curve according to the Kaplan-Meier method and the related Kaplan-Meier estimators will be calculated.

Additional Analyses:

All the analyzes may be stratified by center if recruitment in each center participating in the study is sufficient for such analyzes to be of interest. However, it must be emphasized that this Protocol in no way aims to compare the centers.

For exploratory purposes, the study criteria will also be analyzed depending on patient baseline characteristics:

- Age (in categories)
- Gender
- Diameter of Abdominal Aortic Aneurysm
- Patient status (normal or high surgical risk according to the Afssaps criteria, Appendices 3 and 4)

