Appendix 1: Opinion of HAS dated July 13, 2010

HAUTE AUTORITÉ DE SANTÉ
NATIONAL COMMISSION FOR EVALUATION OF MEDICAL DEVICES
AND HEALTH TECHNOLOGIES
OPINION OF THE COMMISSION

July 13, 2010

Devices : Abdominal Aortic Endoprosthesis (Title III - Chapter 1 - Section 1 - Subsection 2 - paragraph 4 of the list of products and services mentioned in Article L. 165-1 of the Social Security Code)

Pursuant to:

- Decree No. 2004-1419 of 23 December 2004 on the management of products and services mentioned in Article L. 165-13 of the Social Security Code authorizing the Evaluation of Products and Services Commission (CEPP), on its own initiative or at the request of Ministers in charge of Social Security, to reevaluate the expected or actual services of the products or services listed as provided for in Article L. 165-1 (Article 13 of the Decree);
- self-referral to CEPP dated April 5, 2006 relating, in particular, to post-registration study objectives required within the framework of the renewal of registration of Abdominal Aortic Endoprostheses listed under brand name;
- the proposals of the mandated Working Group;

the National Commission for Evaluation of Medical Devices and Health Technologies recommends amending the conditions for renewal of registration of Abdominal Aortic Endoprostheses, listed under the brand name, in the following manner.

Terms of Renewal

CNEDiMETS subjects the renewal of registration of each endoprosthesis to the presentation of results of a specific follow-up study implemented on a cohort of patients representative of the population treated in real life conditions.

The objective of each study is to evaluate the usefulness of the technique by documenting overall mortality, complications (endoleak, migration), the rate of surgical conversion, evolution and rupture of the aneurysm, in the long term, that is, beyond 5 years.

This prospective cohort study shall involve at least 150 patients implanted after registration on the LPPR [List of Reimbursable Products and Services].

The results of the follow-up study shall be forwarded to CNEDiMETS once a year, for consideration.

The evaluation of this follow-up may lead CNEDiMETS to recommend that reimbursement for the EPA concerned be maintained or suppressed.

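### Aneurysm rupture is a stated objective and a renewal requirement, but none of the four protocol criteria lists names it, so the protocol as written yields no separate rupture count or rate

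*Protocol*

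**What the plan says.** The objective in the protocol summary covers "the rate of surgical conversion, the evolution and rupture of the aneurysm, in the long term, that is, 5 years", after overall mortality and the complications endoleak and migration. Section 2 repeats it as bullets, the last being "The evolution and rupture of the aneurysm". SAP 1.1 carries the same objective. Its origin is the health authority's opinion, reproduced in Appendix 1, which asks each study to document "the rate of surgical conversion, evolution and rupture of the aneurysm, in the long term, that is, beyond 5 years". Section 1.1.3 repeats those terms and adds that the follow-up results may lead the authority to recommend keeping or ending reimbursement.

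The protocol lists its criteria four times: in the summary, 3.3, 3.4 and 6.2.2. Each list has the same seven items: all-cause death, aneurysm-related death, evolution of the diameter, endoleak types I to III, migration, surgical conversion and re-intervention. The list in 3.3 closes with "Rate of endovascular or surgical re-intervention". Rupture is not an item in any of them.

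In the definitions under 3.4 and 6.2.2, rupture occurs only as a cause of death. Aneurysm-related death is "any death occurring as a result of a ruptured Abdominal Aortic Aneurysm or following any procedure intended to treat Abdominal Aortic Aneurysm". The planned analysis follows the criteria list: "Each of the rates that match the Study criteria will be analyzed by calculating frequency distributions", with 95% confidence intervals and Kaplan-Meier curves for event rates over time.

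In the visible SAP, section 2.4.3 makes 5-year mortality the primary analysis. The secondary analyses are surgical conversion during the procedure, aneurysm-related mortality, diameter evolution, endoleak, migration and re-intervention. Tables 33 to 44 correspond to these.

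**The concern.** Exclusion of the aneurysm is meant to prevent rupture. Section 1.1.1 links early repair to preventing it and describes it as a common cause of death in these patients. The authority asks for rupture by name, and section 1.2 says the study will meet the authority's requirements.

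Under the protocol, whatever is on the criteria list is measured at each follow-up, given a rate and an interval, and included in the annual report. An outcome that is in the objective but not on the list has no planned measurement and no planned estimate. A report that follows the protocol exactly could therefore be complete against its own criteria and still not say how many patients had a rupture after implantation.

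**Working it through.** The plan states no figure for rupture, so there is none to reproduce. The check has three steps: a comparison of passages, a trace of where a rupture would be counted, and a small illustration of precision.

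**Step 1. Objective against criteria lists.** Splitting the section 2 bullets gives 1 (mortality) + 2 (endoleak, migration) + 1 (conversion) + 2 (evolution, rupture) = 6 components.

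| Component | Summary | 3.3 | 3.4 | 6.2.2 |
|---|---|---|---|---|
| Overall mortality | yes | yes | yes | yes |
| Endoleak | yes | yes | yes | yes |
| Migration | yes | yes | yes | yes |
| Surgical conversion | yes | yes | yes | yes |
| Evolution (diameter) | yes | yes | yes | yes |
| Rupture | no | no | no | no |

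Of 6 × 4 = 24 cells, 20 are filled. The 4 empty cells are all rupture.

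**Step 2. Where a rupture would be counted.**

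| Course of the rupture | Criterion it enters | Identifiable as rupture? |
|---|---|---|
| Fatal | All-cause death and aneurysm-related death | No; pooled with procedure-related deaths, and deaths within 30 days of a procedure count by default |
| Survived and treated | Surgical conversion or re-intervention | No; not labelled by cause |
| Neither fatal nor treated | None | No |

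Evolution of the diameter does not fill the gap. The only event defined for it is growth of more than 5 mm, and the objective names evolution and rupture separately.

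**Step 3. What a reported count would give (illustration only).** The documents contain no rupture rate, so the event counts below are assumed. For 0 events among n patients, the two-sided 95% Clopper-Pearson upper limit is 1 − 0.025^(1/n).

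- n = 180 (planned cohort): 1 − 0.025^(1/180) = 2.03%.
- n = 150 (the authority's minimum, "This prospective cohort study shall involve at least 150 patients implanted after registration on the LPPR"): 1 − 0.025^(1/150) = 2.43%.
- 1 of 180: 0.56% (0.01% to 3.06%). 2 of 180: 1.11% (0.13% to 3.96%).

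These are crude proportions that treat all n patients as evaluable. Deaths and loss to follow-up reduce the effective number and widen the interval.

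The method matters at low counts. Greenwood's variance is S(t)² Σ d/[n(n − d)], summed over event times. With no events it is 0, so the standard Kaplan-Meier interval has zero width and cannot give the 2.0% limit. The SAP shell for survival tables (4.3.3, Type 10) also places its 95% CI under the median; the survival rate line has none.

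**The case against.** **The SAP may already report rupture.** This stands, and it limits the point. A reader might infer from Tables 33-44 that the SAP leaves rupture out. The documents do not support that. SAP 2.1.3 to most of 2.4.1, the safety analysis text, the tables after Table 44 and part of the listings cannot be read. The contents page announces safety analyses, and the adverse-event shell (4.3.2, Type 9) is used by no visible table, so some planned tables are hidden. Rupture may be among them. The protocol lists are complete and unredacted, and the finding rests on them.

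**Rupture is not the only loosely specified component.** Also true. Endoleak and surgical conversion have no definition in 3.4 or 6.2.2 either, so the lack of a definition does not single rupture out; the lack of a name does. Nor is every other component fully served by the visible SAP: Table 34 and SAP 2.4.3.2 cover conversion during the procedure, which does not match a 5-year conversion objective.

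**Fatal rupture has to be established anyway.** Classifying a death as aneurysm-related requires knowing whether a rupture caused it, and treated ruptures enter conversion or re-intervention. The information may therefore exist in the records. A reader might go further and conclude that rupture is not collected, but the eCRF is not among the documents and this is unknown. What remains is that nothing in the protocol requires ruptures to be separated out and counted.

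**Counting six components is a choice.** Section 2 has four bullets, and evolution and rupture share one. Counted that way, the fourth bullet is only half covered, and the gap is the same.

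**Conclusion.** The point holds for the protocol and should be fixed. Rupture is the only objective component absent from all four criteria lists. Followed as written, the protocol gives no separate count or rate for an outcome that the renewal terms ask for.

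The defect is one of coverage. No planned estimate is biased, and the primary 5-year mortality analysis is unaffected. How many ruptures would go unlabelled cannot be stated, because the documents give no rupture frequency. The conclusion rests on the four protocol lists and the definitions in 3.4 and 6.2.2; it assumes nothing about the redacted SAP text or the eCRF.

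**What to change.** Add a criterion, *aneurysm rupture after implantation (fatal or non-fatal)*, with event date and source (imaging, operation or death record), to the protocol summary, 3.3, 3.4 and 6.2.2 and to SAP 2.4.3.2.

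Report:

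- the number of patients with rupture;
- the crude proportion with an exact (Clopper-Pearson) two-sided 95% CI, which remains valid at 0 events;
- a case listing;
- if events occur, a 5-year Kaplan-Meier estimate with its own 95% CI. A cumulative incidence with death as a competing event is optional.

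If a redacted SAP section already reports rupture, align the protocol lists with it.

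The cost is short wording changes in both documents, one table, one listing and possibly one eCRF item. With few events the estimate will be imprecise, and ruptures in patients who fail to return may be missed. Even so, an explicit zero with an upper limit near 2% tells the authority more than no count.
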